9.5.2 Safety Assessments

Patients must be evaluated by a physician or an appropriately trained health care professional at every visit and the evaluation must be documented. The procedures discussed below will be completed at the designated visits. Scheduled safety assessments are not to be administered if the patient is not accompanied by his/her consented caregiver.

9.5.2.1 *Adverse Events*

An AE is any untoward medical occurrence in a patient or clinical investigation patient administered a pharmaceutical product and which does not necessarily have to have a causal relationship with this treatment. An AE can therefore be any unfavorable and unintended sign (including an abnormal laboratory finding, for example), symptom, or disease temporally associated with the use of a medicinal product, whether or not considered related to the medicinal product (ICH-E2A).

For the purpose of data collection for this study, any untoward event that was reported from the time the patient signed the ICF until 30 days after the last dose of treatment is to be considered an AE.

Examples of AEs are as follows:

- Changes in the general condition of the patient
- Subjective symptoms offered by or elicited from the patient
- Objective signs observed by the Investigator or other study center personnel
- All diseases that occur after signing ICF, including any change in severity or frequency of preexisting disease
- Laboratory values that are deemed to be clinically significant by the Investigator
- Physical exam findings, including vital sign measurements, that are deemed to be clinically significant by the Investigator

Please note that medical procedures scheduled prior to consenting, but occurring during the study should not be captured as AEs, but should be listed in the medical history if related to a pre-existing condition.

9.5.2.2 *Causality Assessment*

For each AE, the Investigator must provide an assessment of causal relationship to the investigational product. The causality assessment must be recorded on the appropriate AE reporting page of the patient's eCRF. Causal relationship must be assessed by answering the following question:

Is there a reasonable possibility that the investigational product caused the event?

Yes: **There is evidence to suggest a causal relationship between the investigational product and AE, ie:**

- There is a reasonable temporal relationship between the investigational product and the event, and/or
- The event is unlikely to be attributed to underlying/concurrent disease, other investigational products, or other factors, and/or
- Positive dechallenge and/or rechallenge exist

No: **There is no evidence to suggest a causal relationship between the investigational product and AE, ie:**

- There is no reasonable temporal relationship between the investigational product and the event, or
- The patient did not take the investigational product, or
- The event is likely to be attributed to underlying/concurrent disease, other investigational products, or other factors, or
- The event is commonly occurring in the (study) population independent of investigational product exposure

9.5.2.3 *Severity Assessment*

The Investigator will provide an assessment of the severity of each AE by recording a severity rating on the appropriate AE reporting page of the patient's eCRF. *Severity*, which is a description of the intensity of manifestation of the AE, is distinct from *seriousness*, which implies a patient outcome or AE-required treatment measure associated with a threat to life or functionality (Section 9.5.2.4). Severity will be assessed according to the following scale:

Mild: A type of AE that is usually transient and may require only minimal treatment or therapeutic intervention. The event does not generally interfere with usual activities of daily living

Moderate: A type of AE that is usually alleviated with additional specific therapeutic intervention. The event interferes with usual activities of daily living, causing discomfort but poses no significant or permanent risk of harm to the research participant

Severe: A type of AE that interrupts usual activities of daily living, or significantly affects clinical status, or may require intensive therapeutic intervention

9.5.2.4 *Serious Adverse Events*

An SAE is any untoward medical occurrence that at any dose:

- Results in death
- Is life threatening
- Requires inpatient hospitalization or prolongation of existing hospitalization
- Results in persistent or significant disability/incapacity, or
- Is a congenital anomaly/birth defect

Important medical events that may not result in death, be life threatening, or require hospitalization may be considered serious when, based on appropriate medical judgment, they may jeopardize the patient or subject and may require medical or surgical intervention to prevent one of the outcomes listed in this definition. Examples of such medical events include allergic bronchospasm requiring intensive treatment in an emergency room or at home, blood dyscrasias or convulsions that do not result in patient hospitalization, or the development of investigational product dependency or drug abuse.

Emergency room visits that do not result in hospitalization should be evaluated for one of the other serious outcomes to determine whether they qualify as SAEs.

Preplanned hospitalizations (eg, elective procedures for preexisting conditions that did not worsen, such as cosmetic surgery and hysterectomy) are excluded from SAE reporting.

9.5.2.5 *Reporting Adverse Events and Serious Adverse Events*

At each visit, patients are to be queried regarding any AEs or SAEs that have occurred since the previous visit. Patients will be asked to volunteer information with a nonleading question such as, "How do you feel since your last visit?" Study center personnel will record all pertinent information in the patient's eCRF.

In addition, any SAEs reported by the patient (or patient representative) or otherwise identified by the Investigator after the study period (ie, after 30 days post last dose) should be documented and reported.

All AEs must be recorded on the appropriate AE reporting page of the patient's eCRF whether or not they are considered causally related to the investigational product.

For every AE, the Investigator must:

- Provide an assessment of the seriousness of the event (ie, is it an SAE?), as well as the severity and causal relationship
- Document all actions taken with regard to the investigational product
- Detail any other treatment measures taken for the AE
- Document the outcome of the AE

In addition, patients and caregivers are to be reminded, as described in the ICF and in accordance with Section 9.5.2.1, to notify site personnel of any AEs occurring during the 30-day poststudy period. Any AEs reported by the patient (or patient representative) during this period are to be recorded in original source documents. AEs are also to be recorded in the eCRF if at least one of the following conditions is met: 1) the event meets the criteria for an SAE (see Sections 9.5.2.4 and 9.5.2.6), and/or 2) the event is judged by the Investigator to be potentially causally related to investigational product.

Any AEs that are ongoing at the time of the final protocol-defined study visit will be followed until the condition returns to prestudy status, has resolved or stabilized, or can be explained as being unrelated to the investigational product. If a follow-up visit is deemed necessary for appropriate safety surveillance, it will take place within 30 days of the final protocol-defined study visit.

9.5.2.6 *Immediate Reporting of Serious Adverse Events and Events of Special Interest*

AGN is required to inform worldwide regulatory authorities of SAEs that meet specific criteria. Therefore, AGN must be notified immediately regarding any SAE that occurs after informed consent is obtained.

Within 24 hours of learning of any AE that meets one of the criteria for an SAE, the study center personnel must report the event to Global Drug Safety on the SAE Form for Clinical Trials. The Study Physician may also be notified by telephone.

If, during follow-up, any nonserious AE worsens and eventually meets the criteria for an SAE, that AE should be recorded as a new SAE.

The study center must transmit the SAE Form for Clinical Trials to the SAE fax number shown below. Even if an initial report is made by telephone, the SAE Form for Clinical Trials completed with all available details must still be faxed within 24 hours of knowledge of the event at the study center.

Supplemental information should be submitted as soon as available and may include laboratory results, radiology reports, progress notes, hospital admission and emergency room notes, holding and observation notes, discharge summaries, autopsy reports, and death certificates.

The Investigator is expected to take all therapeutic measures necessary for resolution of the SAE. Any medications or procedures necessary for treatment of the SAE must be recorded on the appropriate pages of the patient's eCRF. All SAEs are to be followed by the study staff until resolution or until the SAE is deemed stable. **AGN may contact the study center to solicit additional information or follow up on the event.**

Fax the SAE Form for Clinical Trials to AGN:

SAE fax number:

Primary: [name]
Back-up: [name]

9.5.2.7 *Reporting of Pregnancies Occurring During the Study*

Study center personnel must report every pregnancy from the time the patient signs the ICF until 30 days after the last dose of investigational product. Within 24 hours of learning of a pregnancy, the study center personnel must report the event to Global Drug Safety on the Clinical Trial Pregnancy Form and fax it to the SAE/Pregnancy fax number stated in Section 9.5.2.6, even if no AE has occurred. Pregnancies in female partners of male patients occurring during the time frame described above must also be reported.

The pregnancy must be followed to term and the outcome reported by completing a follow-up Clinical Trial Pregnancy Form. If the pregnancy is associated with an SAE (eg, if the mother is hospitalized for hemorrhage), a separate SAE Form for Clinical Trials must be filed as described in Section 9.5.2.6 with the appropriate serious criterion (eg, hospitalization) indicated in addition to the Pregnancy Form.

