The paper version of the C-SSRS will be completed at all study visits. At Visit 1 (Screening), the C-SSRS will be completed for the patient's lifetime history of suicidal ideation and behavior ([Appendix VIII](#)). At all other visits, the C-SSRS will be completed for ideation and behavior since the previous visit ([Appendix IX](#)). The C-SSRS will be evaluated and signed at each visit by a qualified staff member (ie, the Investigator or designee that has extensive professional training and experience in assessing mental illness), before the patient leaves the study center.

The patient should not be released from the study center until the results of the C-SSRS are reviewed and the patient is not considered to be at risk. If there is doubt about whether a patient is at risk, the Investigator must obtain appropriate psychiatric consultation. The results of the C-SSRS will be recorded in the eCRF.

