9.9 PROTOCOL DEVIATIONS AND VIOLATIONS

A *protocol deviation* is any change, divergence, or departure from the study design or procedures that is under the Investigator's responsibility and oversight (as defined by regulations) without prior written IRB/IEC approval or favorable opinion of an appropriate amendment and that does not have a major impact on the patient's rights, safety, or well-being, or on the integrity and authenticity of the study data. Deviations may include, but are not limited to, departure from inclusion/exclusion criteria, allowed concomitant medications, dosing, or duration of treatment, failure to follow withdrawal criteria or perform the required assessments at specified time points, scheduling of visits not in accordance with specifications.

Deviating from the protocol is permitted only if absolutely necessary for the safety or clinical management of the patient and must immediately be reported to AGN. Protocol deviations, including those that may be due to the COVID-19 pandemic, should be reported to AGN (either verbally or electronically) in a timely manner from the date of discovery.

Protocol deviations that may impact a patient's rights (eg, failure to obtain informed consent prior to initiating study procedures), safety or well-being (eg, deviations that resulted in an SAE, exposure during pregnancy), or the integrity and authenticity of the study data should be reported to AGN within 24 hours, if possible.

The IRB/IEC must be notified according to the criteria and time period dictated by the IRB/IEC associated with this study.

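### Protocol 9.5.2 bars scheduled safety assessments when the caregiver is absent and does not exempt the C-SSRS, so a patient who attends alone can leave without it

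*Protocol*

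**What the plan says.** Protocol 9.5.2 opens with two instructions. The first is that "Patients must be evaluated by a physician or an appropriately trained health care professional at every visit and the evaluation must be documented". The second is that "Scheduled safety assessments are not to be administered if the patient is not accompanied by his/her consented caregiver". No exception follows the second.

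Two subsections of 9.5.2 then set requirements for every visit:

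- On the C-SSRS (9.5.2.12.2): "The paper version of the C-SSRS will be completed at all study visits", and "The patient should not be released from the study center until the results of the C-SSRS are reviewed" and the patient is judged not to be at risk. If risk is in doubt, the Investigator must obtain psychiatric consultation.
- On adverse events (9.5.2.5): "At each visit, patients are to be queried regarding any AEs or SAEs that have occurred since the previous visit".

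Other provisions bear on a patient who arrives alone:

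- Caregiver attendance at all visits is a condition of entry (5.3.3; 9.3.1, criterion 5).
- Efficacy ratings carry the same caregiver condition (9.5.1).
- Visits may move by 3 days either way (9.5.5).
- The C-SSRS may be done remotely (Protocol front text on remote safety assessments; Section 2.1).
- Section 9.9 counts a failure to "perform the required assessments at specified time points" among deviations, and adds: "Deviating from the protocol is permitted only if absolutely necessary for the safety or clinical management of the patient".

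**The concern.** The caregiver rule is written for the very case in which a patient arrives alone, and for the C-SSRS it points the wrong way. A site that follows 9.5.2 literally withholds the one structured instrument meant to detect suicidal ideation or behavior that is not otherwise apparent. A site that follows 9.5.2.12.2 literally gives it and holds the patient until it is reviewed. The text does not say which instruction governs on the day, or that the visit should be rebooked.

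The patients are 7 to 17 years old and have MDD. Suicidal ideation and behavior are the safety outcomes that 9.10 names for the Data Monitoring Committee. At stake is a delayed or missed suicide-risk check for an individual patient. The trial's efficacy result is not at stake.

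**Working it through.** The plan gives no figure to reproduce here. The check sets the passages side by side, with simple arithmetic on the visit schedule.

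**1. Does the bar cover the C-SSRS and the AE query?** Yes. Both are subsections of 9.5.2. Both are listed as safety measures in the Synopsis and as safety parameters in 9.7.6. The Schedule of Evaluations (Section 2.0) marks each at 9 of 9 visits, so both are scheduled safety assessments.

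**2. Is there an exemption elsewhere?** None was found in the caregiver text (5.3.3, 9.3.1), the remote-visit text (front text, 2.1, 9.1.1), the visit descriptions (9.5.5.1 to 9.5.5.7), 9.9 or the SAP. The remote provisions change the mode of assessment but do not lift the caregiver condition. Section 9.1.1 also reserves remote visits for cases where local guidance, regulations or the patient's needs prevent on-site procedures.

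**3. What can a site do when the patient arrives alone?**

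- Rebook within the window and do everything with the caregiver present. Both rules are met.
- Give the C-SSRS anyway. This departs from 9.5.2.
- Withhold it and do not rebook. A required assessment is missed, and the patient leaves without the review that 9.5.2.12.2 calls for.

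The room to rebook depends on the day of attendance. If the patient comes d days from the scheduled day (−3 ≤ d ≤ 3), 3 − d days remain: 6 at d = −3, 3 at d = 0, and 0 at d = 3.

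**4. What does one withheld check do to the spacing?** On-study C-SSRS weeks (Section 2.0) are 0, 1, 2, 3, 4, 6, 8 and 9. The planned gaps are therefore 1, 1, 1, 1, 2, 2 and 1 weeks. If one postbaseline check is withheld and not rebooked, the gap is the next week minus the previous week:

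| Withheld | Gap between completed checks |
|---|---|
| Week 1 | 2 − 0 = 2 weeks |
| Week 2 | 3 − 1 = 2 weeks |
| Week 3 | 4 − 2 = 2 weeks |
| Week 4 | 6 − 3 = 3 weeks |
| Week 6 | 8 − 4 = 4 weeks |
| Week 8 | 9 − 6 = 3 weeks |
| Week 9 | no later scheduled check |

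The longest case is Week 6 withheld with Visit 6 three days early and Visit 8 three days late: 28 + 3 + 3 = 34 days. If the visit is rebooked within the window instead, the check falls at most 3 days after its scheduled day.

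Before Week 9, the content can be recovered later: "At all other visits, the C-SSRS will be completed for ideation and behavior since the previous visit". This holds if the rater looks back to the last completed form and not merely to the last attendance. What is lost is timeliness.

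**5. Why is Visit 9/SFU the most exposed?** The C-SSRS is scheduled at 7 postbaseline visits (Visits 3 to 9) and efficacy ratings at 6 (Visits 3 to 8). So 7 − 6 = 1 visit, Visit 9, has a C-SSRS but no efficacy ratings (9.5.5.7). The caregiver bar in 9.5.1 therefore gives no separate reason to rebook it. It follows the down-taper or early discontinuation, and no further C-SSRS is scheduled. The remote fallback is also less clear there: Section 2.1 lists Visit 9, but 9.1.1 describes remote conduct for Visits 2 to 8 only.

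**The case against.** The strongest reply is that the rules fit together. Caregivers commit to attend every visit, so a patient who arrives alone is simply rebooked, and the every-visit requirements are met once the caregiver comes. The 3-day window and the spare doses in the blister cards (9.4.2) support this. At Visits 3 to 8 the visit cannot be completed without the caregiver anyway, because efficacy ratings are barred and dosing instructions go to patient and caregiver together. Requiring the caregiver is also protective in itself: that person is a named source of safety information about a depressed child.

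Much of this stands. A reader might infer that the two instructions can never both be followed. The documents do not support that, because rebooking within the window satisfies both. A reader might also infer that a lone patient goes unevaluated. That is not supported either. The bar covers only scheduled assessments, the documented clinician evaluation carries no caregiver condition, consultation is mandatory when risk is in doubt, and 9.9 allows deviations that safety makes absolutely necessary.

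The AE half of the point is minor. AEs are collected until 30 days after the last dose (9.5.2.1), patients and caregivers are reminded to report them in the 30-day poststudy period, and later SAEs are still documented (9.5.2.5). A missed query can be made good at a later contact.

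Visit 9 has safeguards too: all randomized patients must return for it, it has its own ±3-day window (9.5.5.6), and 9.5.5.7 allows a further visit within 30 days of stopping product if one is needed.

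The reply does not remove the gap. No passage instructs rebooking, and rebooking still lets the patient leave that day without the C-SSRS. Clinical evaluation and consultation depend on risk being suspected, whereas the scale is meant to find risk that is not apparent. A routine C-SSRS in a patient who looks well may not meet the 9.9 test of absolute necessity.

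**Conclusion.** The point holds as a patient-safety clarification. Section 9.5.2 bars scheduled safety assessments without the caregiver and does not exempt the C-SSRS, so an unaccompanied patient can leave that day without the structured suicide-risk check. Existing safeguards keep the practical risk limited.

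The frequency is unknown: the documents give no rate of caregiver absence and none is assumed. The size of a single occurrence follows from the schedule. The delay is at most 3 days past the scheduled day if the visit is rebooked within the window. Without rebooking, the gap is 2 to 4 weeks (34 days at the extreme), and after Visit 9 no C-SSRS is scheduled. The longer gaps assume that the caregiver is absent, the visit is not rebooked, no remote C-SSRS is done and no safety deviation is made.

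Nothing here supports an inference about efficacy, power or between-arm bias, and none is claimed.

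**What to change.** Add to Protocol 9.5.2 that:

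- the C-SSRS, AE query and clinical safety evaluation are done at every attended visit, whether or not the caregiver is present;
- caregiver input is then obtained by phone or at a rebooked visit within the window;
- the caregiver or parent/guardian/LAR is contacted before an unaccompanied patient with a positive C-SSRS is released.

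The efficacy rule in 9.5.1 can stay as it is.

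The cost is a short amendment across about 60 centers. Section 9.8 lets an amendment that reduces risk to patients take effect before IRB/IEC review, with written notice and later approval. The downside is that some C-SSRS and AE data would be collected without the caregiver in the room. The benefit is also smaller late in the trial: 9.7.8 reports that 62% of randomized patients had already completed or discontinued at the interim analysis. It remains a cheap improvement for patients still to be seen.

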11.1 ADVERSE EVENTS

Adverse events will be coded by system organ class and preferred term using the *MedDRA*, version 22.0 or newer.

An AE will be considered a treatment-emergent adverse event (TEAE) if the AE began or worsened (increased in severity or became serious) on or after the date of the first dose of investigational product. However, an AE that occurs more than 30 days after the last dose of study intervention will not be counted as a TEAE. Per eCRF instructions, a new AE record will be created with a new AE onset date for any AE that worsens. Therefore, TEAEs can simply be identified as those AEs with recorded onset date on or after the date of the first dose of investigational product and within 30 days after the last dose of investigational product. If more than 1 AE was reported before the date of the first dose of investigational product and coded to the same preferred term, the AE with the greatest severity will be used as the benchmark for comparison with the AEs occurring during the double-blind treatment period or during the double-blind down-taper period that were also coded to that preferred term.

The number and percentage of patients reporting TEAEs in each treatment group will be tabulated by system organ class and preferred term and further categorized by severity and causal relationship to the investigational product, for both the double-blind treatment period and the double-blind down-taper period, separately. If more than 1 AE is coded to the same preferred term for the same patient, the patient will be counted only once for that preferred term using the greatest severity and strictest causality for the summarization by severity and by causal relationship to the investigational product, respectively.

The distribution of TEAEs by severity and causal relationship to the investigational product will be summarized by treatment group separately for the double-blind treatment period and the double-blind down-taper period. Common TEAE during the double-blind treatment period is defined in 2 ways: $\geq 1\%$ of patients in any treatment group and $\geq 2\%$ of patients in any treatment group. The incidence of common TEAEs will be summarized separately by preferred term, and treatment group and will be sorted by decreasing frequency for the levomilnacipran treatment group.

An AE will be considered a treatment-emergent serious adverse event (TESAE) if it is a TEAE that additionally meets any serious adverse event (SAE) criterion.

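### Protocol 9.5.2.5 gives two conflicting eCRF rules for adverse events after the study, while the AE and TEAE definitions stay open to 30 days after last dose

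*Protocol*

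**What the plan says.** Protocol 9.5.2.5 contains two recording rules.

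- General rule: "All AEs must be recorded on the appropriate AE reporting page of the patient's eCRF whether or not they are considered causally related".
- Poststudy rule: patients and caregivers are reminded "to notify site personnel of any AEs occurring during the 30-day poststudy period". Events reported then go into source documents. For entry in the database, the rule is that "AEs are also to be recorded in the eCRF if at least one of the following conditions is met". One condition is seriousness: "the event meets the criteria for an SAE". The other rests on causality: "the event is judged by the Investigator to be potentially causally related to investigational product".

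Neither rule is said to override the other, and the start of the poststudy period is not defined.

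The definitions that use these data run to a fixed point after last dose. Under Protocol 9.5.2.1, for data collection, any untoward event reported from consent "until 30 days after the last dose of treatment is to be considered an AE". SAP 11.1 says that "an AE that occurs more than 30 days after the last dose of study intervention will not be counted as a TEAE", and identifies TEAEs simply from recorded onset dates between first dose and 30 days after last dose. Protocol 9.7.6.1 has the same 30-day cut-off, but first requires the event to occur in the double-blind or down-taper period.

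The SAP does not mention the poststudy restriction, and SAP 18.0 lists no changes from the protocol.

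**The concern.** Read together, the documents declare 30 days after last dose countable, then allow part of that stretch to be collected selectively. The selection depends on the investigator's causality opinion. Protocol 9.5.2.2 points that opinion towards unrelated when an event is likely due to underlying disease or is common in the study population. In depressed children who have just stopped study drug, a nonserious mood or sleep complaint could easily be judged that way. It would then stay in the site's source documents and never reach the analysis database.

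Within the restricted stretch, every nonserious event that does reach the eCRF is related by construction, so a relatedness summary of that stretch would mean nothing. The last scheduled C-SSRS is at Visit 9. After that, AE reports are the only study source the documents show for nonserious psychiatric events.

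**Working it through.** The plan states no figure for the restricted share, so there is none to reproduce. The share follows from a day count.

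**Inputs**
- Double-blind treatment: 8 weeks = 56 days (Protocol 9.1).
- Down-taper: 1 week = 7 days (Protocol 9.1).
- TEAE window: first dose to last dose + 30 days (SAP 11.1).
- Visit 9: at the end of taper, so about 0 days after last dose. Without taper it is about 7 days after Visit 8/ET (Protocol 9.5.5.7). The visit tolerance is ±3 days (Protocol 9.5.5.6).
- Assumption: the restriction starts at Visit 9, and last dose falls at Visit 8/ET for patients who do not taper.

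**Formula**

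Restricted share = (30 − days from last dose to Visit 9) / (dosing days + 30)

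**Results**

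| Patient | Window (days) | Restricted days | Share |
|---|---|---|---|
| Completer, taper | 56 + 7 + 30 = 93 | 30 − 0 = 30 | 32.3% |
| Same, Visit 9 three days late | 93 | 27 | 29.0% |
| Completer, no taper | 56 + 30 = 86 | 30 − 7 = 23 | 26.7% |
| Same, Visit 9 at 4 or 10 days | 86 | 26 or 20 | 30.2% or 23.3% |
| Stops at week 4, taper | 28 + 7 + 30 = 65 | 30 | 46.2% |
| Stops at week 4, no taper | 28 + 30 = 58 | 23 | 39.7% |
| Stops at week 1, taper | 7 + 7 + 30 = 44 | 30 | 68.2% |
| Stops at week 1, no taper | 7 + 30 = 37 | 23 | 62.2% |

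For a pooled figure, take the 17% dropout from Protocol 9.7.9 and assume it is spread evenly over weeks 1, 2, 3, 4 and 6 (0.17/5 = 0.034 each).
- All taper: 30 / [0.83 × 93 + 0.034 × (44 + 51 + 58 + 65 + 79)] = 30 / 87.29 = 34.4%.
- None taper: 23 / [0.83 × 86 + 0.034 × (37 + 44 + 51 + 58 + 72)] = 23 / 80.29 = 28.6%.

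**Which outputs the restriction can reach**
- Under SAP 11.0 the last analysis period for a patient ends at the later of last dose and last assessment, normally Visit 9. SAP 11.1 tabulates TEAEs separately for the double-blind and down-taper periods. A nonserious event after Visit 9 can therefore meet the TEAE definition and still fall in neither table.
- The TESAE summary (SAP 11.1) is unfiltered because all SAEs pass. AEs leading to discontinuation of study drug precede the restriction.
- Not limited by period as written: the COVID-19 TEAE count (SAP 17.2), and the listings of all AEs in patients with potentially clinically significant laboratory, vital sign or ECG values, QTc increases, or suicidal ideation or behavior (SAP 11.2 to 11.5.1).

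**The case against.** The strongest reply is that the two sentences form a general rule and an exception. The general rule follows the instruction to query patients at each visit; the poststudy rule is introduced as an addition and covers spontaneous reports afterwards. That is a fair reading of intent, but the exception is not stated as one. The general rule says all AEs, and the definition in 9.5.2.1 runs to the same 30 days.

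A second reply is that the poststudy period might begin only after the 30 days. The SAE sentence in the same section equates the end of the study period with 30 days post last dose. On that reading the restriction lies wholly outside the TEAE window and the affected share is zero. This is the weaker reading, because the poststudy sentence refers back to 9.5.2.1, whose 30-day window starts at last dose. Sites could still apply either.

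A third reply concerns consequences, and most of it stands. A reader might infer that TEAE incidence in the main tables is understated and the related share inflated. The documents do not show this, since those tables are tied to periods that normally end by Visit 9, and Protocol 9.7.6.1 does not count every event to 30 days. A reader might infer that about a third of events are lost. The figures count days, and no scheduled visit after Visit 9 would produce reports at a steady rate. A reader might infer that the filter acts differently by arm. That is conjecture: treatment and taper are double-blind, and no figure supports it. A reader might infer that serious suicidality could go unrecorded. SAEs, including medically important events, always enter the eCRF, and the C-SSRS is repeated at Visit 9.

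**Conclusion.** The concern holds as a conflict between recording rules, and between those rules and the 30-day definitions. Its demonstrated effect on the results is limited. If the restriction starts at Visit 9, about 32% of the TEAE window in days for a tapering completer, or 27% without taper, is collected selectively. The share is higher for early terminators. What is lost is nonserious events judged unrelated, and these remain in source documents, so they can be recovered before database lock.

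SAE counts are untouched, and the main period-based TEAE tables are probably little affected. The COVID-19 TEAE count, the listings of all AEs in flagged patients, and any summary built on the SAP's 30-day definition alone would be incomplete, with nothing in the output to show it. The conclusion rests on reading the poststudy period as starting at Visit 9, which the text favours but does not settle. The documents give no basis for an event-level estimate.

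**What to change.** Reconcile the sentences in one of two ways.

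1. Preferred: delete the two-condition sentence in Protocol 9.5.2.5 and enter in the eCRF every AE reported up to 30 days after last dose. The restricted share then falls to 0 of 93 days with taper and 0 of 86 without, and collection matches Protocol 9.5.2.1 and SAP 11.1.
2. Alternative: keep limited collection, but define the poststudy period as starting after Visit 9 and make it an explicit exception to the general rule. In Protocol 9.7.6.1 and SAP 11.1, end the TEAE window for nonserious AEs at Visit 9 and keep 30 days for SAEs. The COVID-19 count and the listings should then state that cut-off.

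The first option costs a sentence in the protocol or eCRF guideline and probably a few extra entries from events already in source documents. The second costs a definition and two edits, and gives up nonserious events after Visit 9. Neither changes visits or treatment. Neither cures spontaneous under-reporting after Visit 9; the first removes only the causality filter.
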